With the exception of AChE inhibitors, the complement inhibitor eculizumab, and a liquid formulation of azathioprine, which have received regulatory approval in Europe for the treatment of gMG, all other existing therapies are used off-label [Vyvgart EPAR].

In the United States (US), efgartigimod is approved for the indication of gMG in adult patients who are AChR antibody positive and in the EU it is approved as an add-on to standard therapy for the treatment of adult patients who are AChR antibody positive.

The recommended dose of efgartigimod is 10 mg/kg as a 1-hour intravenous infusion to be administered in cycles of once weekly infusions for 4 weeks. Subsequent treatment cycles are administered according to clinical evaluation. The frequency of treatment cycles may vary by patient.

In the EU Risk Management Plan (RMP) for efgartigimod, serious infections, is considered to be an important potential risk. As efgartigimod induces a transient lowering in IgG levels, there is a potential

risk for infections associated with the lowered IgG levels. In the randomized placebo-controlled study of 167 patients ARGX-113-1704, 84 patients with gMG were exposed to efgartigimod and the most frequently observed adverse reactions were upper respiratory infections (10.7% in the efgartigimod patients and 4.8% in the placebo patients) and urinary tract infections (9.5% in the efgartigimod patients and 4.8% in the placebo patients). In the patients who received efgartigimod, these events were \leq Grade 2 according to the Common Terminology Criteria for Adverse Events (CTCAE). Overall, treatment emergent infections were reported in 46.4% of patients treated with efgartigimod and 37.3% of patients treated with placebo. The frequency of infections in the efgartigimod treated patients did not increase with repeated cycles of treatment. There were no serious infections or opportunistic infections in the efgartigimod treated patients. This study will evaluate the occurrence of serious infections in gMG patients treated with efgartigimod in the real world setting under conditions of normal clinical practice compared to gMG patients who are not treated with efgartigimod.

During clinical development of the IV formulation, in the efgartigimod phase 3 placebo-controlled 26 week clinical study, ADAPT, there were 2 reported neoplasm events, 1 (1.2%) in the efgartigimod treatment arm and 1 (1.2%) in the placebo treatment arm.

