Malignancy	Any adverse event (AE) within the Standardised MedDRA Query (SMQ) Malignancies (Narrow) .	Proportion of patients who report events of malignancy during the course of the study in the efgartigimod treated cohort compared to the non-efgartigimod cohort. Incidence rate of events of malignancy per patient-years exposed in the efgartigimod treated cohort compared to the non-efgartigimod cohort.
Adverse event (AE)	Any untoward medical occurrence in a patient administered a pharmaceutical product or device and that does not necessarily have a causal relationship between the product and the event. An AE can, therefore, be any unfavorable or unintended sign (including an abnormal laboratory finding) or symptom temporally associated with a medicinal product, whether or not related to the medicinal product.	Proportion of patients who report AEs during the course of the study in the efgartigimod treated cohort compared to the non-efgartigimod cohort. Incidence rate of AEs per patient-years exposed in the efgartigimod treated cohort compared to the non-efgartigimod cohort.
Serious adverse event (SAE)	As per definition in Section 11.	Proportion of patients who report SAEs during the course of the study in the efgartigimod treated cohort compared to the non-efgartigimod cohort. Incidence rate of SAEs per patient-years exposed in the efgartigimod treated cohort compared to the non-efgartigimod cohort.

AEs (serious and non-serious) in immunocompromised patients
	
Immunocompromised definition (moderate or severe) based upon Centre for Disease Prevention (CDC) People Who Are Immunocompromised CDC.
	
Proportion of AEs/SAEs reported in immunocompromised patients and immunocompetent patients in the efgartigimod cohort.
 
Incidence rate of AEs/SAEs per patient-years exposed in immunocompromised patients and immunocompetent patients in the efgartigimod cohort.

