
AEs (serious and non-serious) in patients treated with monoclonal antibodies
	
Patients receiving monoclonal antibodies other than FcRn (e.g., adalimumab, tocilizumab, ixekizumab, rituximab) within 6 months prior to efgartigimod administration.
	
Proportion of AEs/SAEs reported in patients treated with monoclonal antibodies vs patients not treated with monoclonal antibodies in the efgartigimod cohort.
 
Incidence rate of AEs/SAEs per patient-years exposed in patients treated with monoclonal antibodies vs patients not treated with monoclonal antibodies in the efgartigimod cohort.

AEs (serious and non-serious) in patients treated with live attenuated vaccine
	
Patients receiving live/attenuated vaccine (e.g., live-attenuated flu vaccine, measles, mumps and rubella, polio, smallpox, chickenpox, yellow fever, Japanese encephalitis, shingles, rotavirus) in the period of 4 weeks prior to or 2 weeks after efgartigimod administration.
	
Proportion of AEs/SAEs reported in patients who have received live/attenuated vaccine vs patients who have not received live/attenuated vaccine in the efgartigimod cohort.
 
Incidence rate of AEs/SAEs per patient-years exposed in patients who have received live/attenuated vaccine vs patients who have not received live/attenuated vaccine in the efgartigimod cohort.

AEs (serious and non-serious) in patients with moderate to severe renal impairment
	
Moderate renal impairment: eGFR 30-59 mL/min/1.73 m² Severe renal impairment: eGFR < 30 mL/min/1.73 m²
	
Proportion of AEs/SAEs reported in patients with moderate renal impairment vs patients who have normal renal function in the efgartigimod cohort.
 
Incidence rate of AEs/SAEs per patient-years exposed in patients with moderate renal impairment vs patients who have normal renal function in the efgartigimod cohort.
 
Proportion of AEs/SAEs reported in patients with severe renal impairment vs patients who have normal renal function in the efgartigimod cohort.

		Incidence rate of AEs/SAEs per patient-years exposed in patients with severe renal impairment vs patients who have normal renal function in the efgartigimod cohort.
--	--	--

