Balance of the baseline measures, including age, MG-ADL score and region matched at enrollment and other demographic and disease characteristics, will be assessed. The imbalanced measures which are considered to be potential confounders based on clinical judgement will be added to the above base models as covariates. If a large number of imbalanced potential confounders are identified after the enrollment is complete, a propensity score method will be applied instead. More details will be given in the SAP.

Subgroup analyses will be performed using descriptive statistics on the subset of patients who remained on efgartigimod throughout the duration of the PASS. In addition, subgroup analyses of treatment cycle per year or administration per year (four administrations in one cycle if not interrupted), subgroup analyses of time since the last administration of efgartigimod prior to the event occurrence in intervals of every 4 weeks will be performed, and subgroup analysis of patients using efgartigimod as add-on or single treatment will be performed if sample size allows. Since one patient may have multiple same events with different time to the last administration, one patient may be assigned to multiple time intervals.

Events of Interest

Statistical analysis of malignancy and other events of interest will follow the same method as those for serious infections

Exploratory objectives

Descriptive statistics will be used to summarise the long-term safety of efgartigimod for specific subgroups. The number and percentage of patients with AEs/SAEs will be presented. The rate per person-year exposure with a 95% CI will be constructed using asymptomatic normal approximation. This will be done for the following subgroups:

- immunocompromised patients and immunocompetent patients.
- patients treated with monoclonal antibodies and patients not treated with monoclonal antibodies.
- patients who have received live/attenuated vaccine and patients who have not received live/attenuated vaccine.
- patients with moderate to severe renal impairment and patients with normal renal function or mild renal impairment.

Missing values

No imputation will be applied to occurrence of serious infection, malignancy or other safety events.

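### The four exploratory subgroups are assessed only by all AEs and SAEs; the protocol does not commit to reporting serious infection within any of them

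*Protocol*

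**What the plan says.** Table 2 in section 9.3 gives each exploratory subgroup its own row, with titles such as "AEs (serious and non-serious) in immunocompromised patients" and "AEs (serious and non-serious) in patients treated with live attenuated vaccine". The measure in each row is a proportion and an incidence rate of AEs/SAEs, for example "Proportion of AEs/SAEs reported in immunocompromised patients and immunocompetent patients in the efgartigimod cohort" and "Proportion of AEs/SAEs reported in patients treated with monoclonal antibodies vs patients not treated with monoclonal antibodies in the efgartigimod cohort". The live-vaccine and renal rows follow the same pattern.

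Section 9.7, Exploratory objectives, repeats the choice for the same four subgroups: "Descriptive statistics will be used to summarise the long-term safety of efgartigimod for specific subgroups", and then "The number and percentage of patients with AEs/SAEs will be presented", with a rate per person-year and a 95% CI.

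Serious infection and malignancy have their own rows in Table 2, but those rows compare the efgartigimod cohort with the non-efgartigimod cohort only. Section 7 gives the standing of infection: "In the EU Risk Management Plan (RMP) for efgartigimod, serious infections, is considered to be an important potential risk". The Coding paragraph of section 9.7 promises AEs by SOC and PT in the Safety Population and does not mention the subgroups.

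**The concern.** The subgroup outcome is not left open for the SAP. Table 2 pre-specifies it and section 9.7 restates it. An SAP could follow both exactly and never show serious infection in immunocompromised patients.

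Table 2 defines serious infection as an SAE in a single SOC, so it is one component of the subgroup measure. If the other components do not differ between groups, adding them pulls the ratio towards 1. A report could then show similar AE/SAE figures in a subgroup whose serious-infection risk was materially higher, and this part of the missing information in the risk management plan would stay unanswered.

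**Working it through.** **The plan's own figures.** The protocol states no figure for the exploratory subgroups. The nearest is Table 4: 20% against 31%, 270 per arm, two-sided 0.05. The normal-approximation formula gives 83.65%, against 84% stated. The other Table 4 rows also reproduce, and nothing here disputes them.

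**Step 1: dilution of a proportion.** From section 9.5, take 20% of patients with a serious infection, and double it to 40% in the subgroup. Let q be the probability of any other event of the type counted, independent of infection and equal in both groups. The documents do not give q, so a range is shown. Then P(any event) = 1 − (1 − p)(1 − q).

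| Outcome | q | Reference | Subgroup | Ratio |
|---|---|---|---|---|
| Serious infection | – | 20% | 40% | 2.00 |
| Any SAE | 20% | 36% | 52% | 1.44 |
| Any SAE | 40% | 52% | 64% | 1.23 |
| Any SAE | 60% | 68% | 76% | 1.12 |
| Any AE | 80% | 84% | 88% | 1.05 |
| Any AE | 90% | 92% | 94% | 1.02 |
| Any AE | 95% | 96% | 97% | 1.01 |

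Example: with q = 40%, 1 − 0.8 × 0.6 = 52% and 1 − 0.6 × 0.6 = 64%.

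Starting instead from the 6.2% seen in ADAPT+ (section 9.5) and doubling to 12.4%, the any-SAE ratio is 1.20 at q = 20% and 1.09 at q = 40%.

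**Step 2: visibility on the proportion scale.** Take 270 efgartigimod completers with an assumed 20% subgroup (54 against 216) and the same formula as for Table 4. The chance of a significant excess is 84% on serious infection; 58%, 35% and 19% on any SAE at q = 20%, 40% and 60%; and about 6% on any AE at q = 90%. With a 10% subgroup (27 against 243) the figures are 64%; 37%, 21% and 12%; and about 4%. These count only the tail in the direction of excess.

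**Step 3: visibility on the rate scale.** Assumptions, none from the documents: 3 AEs, 0.2 SAEs and 0.05 serious infections per patient-year, a 10% subgroup and between-patient variance 1. Follow-up is T = 7.5 years, the midpoint of the protocol's 5 to 10, with no drop-out. The subgroup is 10% of 340, so 34 against 306. Doubling serious infection adds 0.05 to each subgroup rate.

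Var(log ratio) = (1 + r₁T)/(n₁r₁T) + (1 + r₂T)/(n₂r₂T), where r₁ and r₂ are the subgroup and reference rates.

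- Serious infection, 0.10 against 0.05: variance 1.75/25.5 + 1.375/114.75 = 0.0806, SE 0.284. z = ln 2/0.284 = 2.44. The chance that the 95% CI excludes 1 is 68%.
- SAEs, 0.25 against 0.20 (ratio 1.25): variance 2.875/63.75 + 2.5/459 = 0.0506, SE 0.225. z = 0.223/0.225 = 0.99. Chance 17%.
- AEs, 3.05 against 3.00 (ratio 1.02): variance 23.875/777.75 + 23.5/6885 = 0.0341, SE 0.185. z = 0.0165/0.185 = 0.09. Chance 3.1% in the upper tail plus 2.0% in the lower, about 5%.

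Two other AE/SAE/serious-infection rate sets give, in the same order as the bullets, 61%, 16% and 5% (rates 2, 0.15, 0.0376) and 78%, 23% and 5% (rates 3, 0.25, 0.0753).

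**The case against.** **This is SAP detail.** Section 9.7 defers analysis detail to the SAP, the objectives are exploratory and descriptive, and the data are collected either way. It stands that nothing irreversible is fixed, which keeps the priority modest. It does not remove the point, because the protocol names the subgroup outcome itself, twice.

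**The SOC/PT tables could show it.** All analyses use the Safety Population, and the subgroups lie within it, so a SOC breakdown by subgroup is compatible with the text. That stands. A reader might infer that serious infection will not be tabulated in the subgroups, but the protocol only fails to commit to it. Nor does the statement that other events of interest follow the serious-infection method add infection to the subgroup rows, since it carries over a method.

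**Infection is not why these subgroups were chosen.** A reader might infer that it is. Section 7 does not say so: it gives missing information as the reason, because the drug had not been studied in these patients. Infection is named as a risk for efgartigimod overall, and the stated objective in each subgroup is safety in general.

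**An effect on SAEs would not be hidden.** Correct. On the 20% assumption, a doubling still leaves an 8 to 16 point difference in any SAE. Only on all AEs does it nearly vanish.

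**Power is a poor yardstick for descriptive analyses.** Fair. The percentages measure how visible a signal would be, not the properties of a planned test. The rates, variance and subgroup sizes are assumed. The rate model also ignores the protocol's 20% drop-out, and immunocompromised patients may well exceed 10%, because section 7 notes that gMG patients take immunosuppressants concomitantly.

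**Conclusion.** The point holds in this form: Table 2 and section 9.7 pre-specify only AEs/SAEs for the four exploratory subgroups, and no section commits to serious infection within any of them. Under the assumed background rates, a doubled serious-infection risk is almost invisible on all AEs and attenuated, not hidden, on SAEs. The proportion model and the rate model show the same ordering. The exact percentages depend on rates and subgroup sizes that the documents do not give, but the direction does not: adding events unrelated to subgroup membership can only shrink the ratio. This is an inexpensive improvement to an exploratory part of the plan. It does not affect the primary comparison or the sample size.

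**What to change.** In the four subgroup rows of Table 2, and in section 9.7 under Exploratory objectives, add serious infection as a named descriptive outcome: number and percentage of patients, and rate per person-year with 95% CI. Use the serious-infection definition already in Table 2. Keep AEs/SAEs as they are, and add malignancy where counts allow.

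No new data are needed, since all AEs are collected and MedDRA-coded. The cost is a few more tables. Counts will be sparse in small subgroups such as live-vaccine recipients, so those intervals will be wide. Naming the outcome before the year 4 interim report avoids the appearance of a choice made after seeing results.

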9.8 Quality Control

argenx has ethical, legal, and scientific obligations to conduct this study in accordance with established research principles and applicable regulatory guidelines. As such, in order to fulfil these obligations and to maintain current knowledge of the study progress, the Contract Research Organisation (CRO) monitors or representatives will regularly contact the clinical sites either by telephone or in-person visits. Regular inspection of the study data will be conducted in order to assess patient enrolment, compliance with protocol procedures, and completeness and accuracy of data entered on the study. Verification of eCRF data against original source documents, and occurrence of SAEs may be done at selected sites and/or for selected patients.

9.8.1 Monitoring

Monitoring details describing strategy, including definition of trial critical data items and processes (e.g., risk-based initiatives in operations and quality such as risk management and mitigation strategies and risk-based monitoring), methods, responsibilities, and requirements, including handling of noncompliance issues and monitoring techniques (central, remote, or on-site monitoring) are provided in the monitoring plans.

9.8.2 Inspection and Auditing Procedures

The purpose of an audit or inspection is to assess whether ethics, regulatory, and quality requirements are fulfilled.

argenx or its representative may conduct audits at the clinical sites including, but not limited to, presence of required documents, the informed consent process, and comparison of case report forms (CRFs) with source documents. All medical records and source data must be available for audit. The site agrees to participate with audits conducted at a convenient time in a reasonable manner.

Government regulatory authorities may also inspect the site during or after the study. Site personnel should contact argenx immediately if this occurs and should cooperate fully with regulatory authorities or other audits conducted in a reasonable manner.

9.8.3 Source Document Maintenance

Source documents contain the results of original observations and activities of a clinical investigation. Source documents include, but are not limited to, medical records, computer printouts, screening logs, and recorded data from automated instruments.

All source documents from this study will be maintained by the site and made available for inspection by authorized persons. The original signed informed consent form (ICF) for each patient shall be filed with records kept by the site and a copy shall be given to the patient.

9.8.4 Record Maintenance

Records will be retained in accordance with the applicable local regulations. All essential study documents, including records of patients, source documents, signed ICFs, and eCRFs, must be kept by the Investigator for at least 10 years from study termination/completion or until instructed in writing by argenx that records may be destroyed or forwarded to argenx. The Investigator shall take responsibility for maintaining adequate and accurate hard copy source documents of all observations and data

generated during this study. Such documentation is subject to audit by argenx or its representatives, and inspection by regulatory authorities.

If an Investigator moves, withdraws from the study, or retires, the responsibility for maintaining the records must be transferred to another person who will accept responsibility. Notice of transfer must be made to and agreed to by argenx.

9.9 Limitations of the Research Methods

Patient-selection bias is a consideration, as motivation to consent to join the study can vary between patients for different reasons. Also, if prescribers and patients are not willing to participate, selection bias may occur, resulting in limited generalisability of the results. All eligible patients at each site will be invited to participate minimising the selection bias. Sites will maintain a log of eligible patients who are not participating in the study and the reasons for non-participation. This data will be provided in aggregate and anonymously to argenx for evaluation of differences between participants and non-participants.

Furthermore, the characteristics of the enrolled population will be analysed after study enrolment is completed; baseline characteristics will be compared to the characteristics of the MG population from real world studies in the literature to identify any potential differences. Information on this comparison will be added to the SAP.

This study is observational in nature and will gather data on standard clinical practice without the constraints of a clinical trial setting. Consequently, there are no protocol mandated procedures, and the collection of data will be limited to what is undertaken in normal clinical practice. This may result in missing data if a procedure has not been performed. This risk has been minimised by ensuring variables are limited to meet the study objectives and are aligned, as far as is possible, to the expected normal clinical practice. The handling of missing data will be specified in the SAP. It would be considered whether a complete records' analysis would be valid, or whether multiple imputation or an alternative approach would likely offer benefits as well as consider a sensitivity analysis regarding the missingness mechanism. The results will be reported, including a description of the missing data, details on how the missing data were addressed, and the results from all analyses.

The study design includes an efgartigimod cohort and a comparator cohort of non-efgartigimod treated patients. The duration of the study is a maximum of 10 years (5 years of enrolment and 5 years of follow up). Over this time period, standard of care for the treatment of gMG is likely to evolve with the introduction of new medicinal products such as ultomiris (recently approved) and rozanolixizumab and zilucoplan (currently under review with an approval expected by end of 2023) and the potential for patients to switch treatments during this time. The comparator group, and indeed the efgartigimod group, will therefore be heterogenous in terms of treatments, thus limiting the interpretability of the results.

Furthermore, in countries where efgartigimod is marketed, it is likely that the efgartigimod cohort and the comparator cohort will differ in terms of disease severity with the more severe patients receiving efgartigimod. Thus, there will be an inherent selection bias. This could be solved by recruiting the comparator patients from countries where efgartigimod is not marketed. However, this will introduce further biases in terms of differing standards of care.

9.10 Other Aspects

Not applicable.

10. PROTECTION OF HUMAN PATIENTS

Prior to any data collection under this protocol, a written ICF must be signed by the patient/legal guardian in accordance with local practice and regulations. Information about the study will be explained to the patient/legal guardian where appropriate including advice that the patient can withdraw from the study at any time. A copy of the ICF, signed and dated by the patient/legal guardian, must be given to the patient/legal guardian. Confirmation of a patient/legal guardian's informed consent must be documented in the patient's medical records prior to any data collection under this protocol. The ICF must not be altered without the prior agreement of the relevant IRB/IEC and argenx.

The participant must be informed that his/her personal study-related data will be used by the Sponsor in accordance with local data protection law. The level of disclosure must also be explained to the participant who will be required to give consent for their data to be used as described in the informed consent.

The participant must be informed that his/her medical records may be examined by auditors or other authorized personnel appointed by the Sponsor, by appropriate IRB/IEC members, and by inspectors from regulatory authorities.

Participants will be assigned a unique identifier. Any participant records or datasets that are transferred to the Sponsor will contain the identifier only; participant names or any information which would make the participant identifiable will not be transferred.

Documents that are not for submission to the study (e.g., ICF), will be maintained by the site in strict confidence, except to the extent necessary to allow monitoring by argenx or its representative, and auditing by argenx and regulatory authorities. No documents identifying patients by name will leave the clinical site and patient identity will remain confidential in all publications related to the study.

Prior to the collection of any study related data, IRB/IEC approval of the protocol, informed consent, and all patient enrolment materials will be obtained in each country and for each site, as applicable. The study will be conducted in accordance with the ethical principles originating from the Declaration of Helsinki, applicable privacy laws, and local regulations for each participating site.

This study will be conducted in accordance with the Guidelines for Good Pharmacoepidemiology Practices issued by the International Society for Pharmacoepidemiology, the Guide on Methodological Standards in Pharmacoepidemiology issued by The European Network of Centres for Pharmacoepidemiology and Pharmacovigilance (ENCePP), Guideline on Good Pharmacovigilance Practices Module VIII Post Authorisation Safety Studies and the Declaration of Taipei.

